IRB Research Protocol

Title: STOP-TIC Study: Strengthening Tourette Treatment Options Using TMS to Improve CBIT

NCT: 04795908

*Please note this is the original IRB document with the intended plan.

Background: Tourette Syndrome (TS) is characterized by multiple motor and at least one vocal tic persisting for at least one year.^{1,2} Up to 20% of patients with TS have persistent tics during adulthood.^{2,3} These tics can lead to impaired quality of life, social embarrassment, dysfunction in completing daily tasks, and complex tics can lead to pain or injuries.^{4,5} Current treatments for TS have limitations: pharmacologic treatments are limited by their side effect profile and incomplete efficacy, and the evolving therapy of deep brain stimulation is an invasive surgery and not appropriate or feasible for most TS patients.⁵⁻⁷ Comprehensive behavioral intervention for tics (CBIT) is an effective intervention for TS⁸⁻¹⁰; however, randomized controlled studies have shown less than 40% reduction of tic symptoms in adult patients with TS.¹⁰⁻¹² Therefore, there is a critical need to potentiate the benefits of CBIT, in order to open the door for innovative treatments that can improve the quality of life for patients with TS.

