Specific Aim #1: Determine the clinical effects of rTMS combined with CBIT in TS.

The clinical effects of active rTMS + CBIT on tics and comorbid nonmotor symptoms will be determined. Tics will be examined with the standardized Yale Global Tic Severity Scale (YGTSS) and the modified Rush Videotape Tic Rating Scale (mRVTRS), and co-morbid symptoms with the Beck Depression Inventory (BDI), Beck Anxiety Inventory (BAI), Yale-Brown Obsessive Compulsive Scale (Y-BOCS) and Adult ADHD Self-Reports Scale (ASRS). Quality of life will be assessed with the Gilles de la Tourette Syndrome – Quality of Life scale (GTS-QOL). I hypothesize that compared to baseline (T0), there will be greater reduction in tics (**Aim 1a**) and associated co-morbid symptoms and improvement of quality of life (**Aim 1b**) at T1 and T2. I also hypothesize that the accelerated protocol will be safe and well tolerated in this patient population (**Aim 1c**).

Specific Aim #2: Determine the physiological effects of rTMS combined with CBIT in TS.

The physiological effects of active rTMS + CBIT will be determined using TMS and fMRI techniques. Cortical excitability will be determined with established TMS single and paired pulse paradigms including RMT, CSP, and SICI (**Aim 2a**), and resting state fMRI will be used to monitor the blood oxygen level dependent (BOLD) activity and connectivity of the SMA (**Aim 2b**). I hypothesize that the change in TMS measures will significantly improve and BOLD activity on fMRI will decrease over SMA at T1 and T2, compared to baseline and will correlate with the clinical improvements as outlined in Specific Aim #1.

RESEARCH PLAN AND METHODOLOGY: Patients with a diagnosis of Tourette's syndrome at our movement disorders center will be enrolled. Diagnosis of TS will be established in accordance with the Diagnostic and Statistical Manual of Mental Disorders, 5th edition (DSM-5).

Inclusion Criteria: Any patient diagnosed with Tourette Syndrome > 18 years of age with moderate tic severity. Participants will be allowed to continue oral medications that they are taking for TS concurrently but will not be allowed to change their concurrent medication regimen throughout the duration of the study.

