Exclusion Criteria: 1) Presence of metallic objects or neurostimulators in the brain, 2) pregnancy, 3) history of active seizures or epilepsy, 4) contraindications to receiving fMRI, such as claustrophobia 5) inability to participate in CBIT due to other underlying cognitive or medical condition

[figure not shown]

Figure 1. Study design and timeline. TS patients with moderate severity symptoms will undergo active rTMS followed by 10 weeks of tele-CBIT. Clinical, physiology measures, and imaging will be collected at three time points (baseline/T0, T1, T2).

Enrollment: Our target is to enroll 20 total patients in the study. In order to enroll 20, we will need to screen more than that number. We anticipate that we will need to screen 64 patients in order to find 24 that are eligible for enrollment. Of those 24, we anticipate that 4 will choose not to participate in the study.

IRB approved informed consent will be obtained. The study procedures will be explained, and subjects will have a detailed medical history and neurological examination. Patients will have primary and secondary outcome measures performed at four time

points: Baseline (T0), following rTMS (T1), and following CBIT (T2) (Figure 1). The study protocol will take place over approximately 11-12 weeks. Details of specific parts of the protocol are included below.

Primary Outcome: Tic severity will be measured with YGTSS and mRVTRS. Videos of participants will be recorded at T0, T1, and T2, which will be scored by two independent blinded raters.

Secondary Outcomes: BDI, BAI, Y-BOCS, ASRS, and GTS-QOL; TMS, EEG, and fMRI outcomes.

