rTMS protocol: rTMS will be delivered using a NeuroStar TMS therapy system (Neurotronics, Malvern, PA). The resting motor threshold (RMT) will be defined as the lowest stimulation intensity required to evoke a 50 μ V potential in a target muscle (i.e. first dorsal interosseous muscle/FDI). A figure of eight coil will be used to deliver the stimulation. Patients will be seated in a comfortable reclined chair. The neurostimulation protocol will include 1-Hz rTMS over the bilateral SMA at 110% RMT. The SMA will be identified as 4 cm anterior to the vertex (Cz in standard 10-20 EEG setup). Each session will consist of 6 trains lasting 5 minutes each (300 pulses per train) with an intertrain interval of 1 minute for a total duration of 35 minutes (1800 pulses). Patients will receive 4 sessions each day on 4 consecutive days for a total of 16 sessions. Daily duration of this study protocol should last approximately 170 minutes including a 10 minute break in between each session (Figure 2). Constant coil position will be continuously monitored during the experiment. During rTMS, all participants will wear earplugs in order to protect the ears from the acoustic artefact associated with the discharge of the stimulation coil.

[figure not shown]

Figure 2. A schematic drawing representing a portion of an rTMS session. Each train consists of 300 pulses over 5 minutes (blue) and each intertrain interval (ITI) lasts for 1 minute without pulses (orange). Each session contains 6 trains alternating with an ITI. Patients will undergo 4 sessions per day, to be repeated for 4 consecutive days.

[figure not shown]

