CBIT protocol: All CBIT sessions will be conducted by an occupational therapist ([name], OTD, OTR/L) who is a certified therapist in CBIT. Patients will have the option of having the first introductory CBIT sessions scheduled in-person since they will already be at the center for rTMS and outcome measures. For convenience, all other CBIT sessions will occur through a secure telemedicine platform. Each CBIT session will last approximately 1 hour. Following CBIT protocol, there will be 8-10 tele-CBIT sessions over 10 weeks, at the therapist's discretion. Each session will be individualized to each patient's needs depending on tic type and severity.

EEG protocol: High-Density EEG using 128 electrodes as the setup will be implemented. Each EEG session should last about 1 hour. Patients will be seated comfortably in a chair and a cap will be stretched across the scalp. This cap has 128 contacts where the electrodes will be connected using biosoluble glue. The electrodes will be placed appropriately by a clinician or technician trained to place the EEG electrodes. The patient's electrical activity will be recorded under two conditions: at rest and asking the patients to voluntarily suppress their tics (Figure 3B and D).

Safety: Since the most important safety concern with rTMS is the possibility of seizure, participants with active seizure disorder or those at increased risk of seizure will be excluded. Low frequency protocols carry less risk of seizure as compared to high frequency protocols given that high frequency generates cortical excitability.⁴⁷ In spite of the theoretically increased risk of seizure in accelerated rTMS protocols, several accelerated high-frequency protocols have been safely performed in other patient populations and have been tolerated well by patients without evidence of increased adverse events.⁴²⁻⁴⁵ A similar protocol to the one proposed in this study, using the same TMS system that I will be using, has been safely completed in the pediatric Tourette's population.³⁴ Patients will be screened prior to admission into the study, and those at risk for adverse reactions will be excluded. Those selected for participation will be monitored closely for adverse events. Other mild side effects that participants may experience secondary to TMS include transient eye pain, toothache, muscle twitch, facial pain, neck stiffness, and pain or discomfort at the application site and skin.

Clinical Assessments:

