Yale Global Tic Severity Scale (YGTSS): This is a tool used to quantify the severity of tics through a semi-structured interview by assessing 5 components: number, frequency, intensity, complexity, and interference.

Modified Rush Videotape Tic Rating Scale (mRVTRS): This is a tool used by an objective examiner to quantify the severity of a patient's tics by rating the number of body areas affected, motor tic frequency, phonic tic frequency, motor tic severity, and phonic tic severity, each on a 0 through 4 score by watching a video of the patient.

Beck Depression Inventory (BDI): This is a 21-question survey evaluating depression in patients on a 0 to 3 scale.

Beck Anxiety Inventory (BAI): This is a 21-question survey evaluation anxiety in patients on a 0 to 3 scale.

Yale-Brown Obsessive Compulsive Scale (Y-BOCS): This is a 10 question survey which rates components of obsessive thoughts or compulsive behavior and each question is rated on a 0 through 4 scale.

Adult ADHD Self-Report Scale (ASRS): This is an 18-question survey which asks patients to rate levels of attention, concentration, and organization as applied to daily tasks.

Gilles de la Tourette Syndrome – Quality of Life scale (GTS-QOL): This is a 27-question survey that asks patients to rate how their tics and abnormal movements affect their quality of life.

Patients will have primary and secondary outcome measures performed at four timepoints: Baseline (T0), following rTMS (T1), and following CBIT (T2). The study protocol will take place over approximately 11-12 weeks. All events related to the study procedure will take place within +/- 14 days of the expected timeline, with more details below (Figure 4). Patients will be compensated for their hotel stay during the 4 consecutive days of rTMS, and they will also receive compensation following completion of their time in the study in its entirety.

Figure 4. Timeline of study events and expected study activities at each timepoint.

Study Events (to occur +/- 14 days)	Screening	Baseline (T0)	rTMS protocol (4 days)	Post-TMS (T1)	CBIT (10 weeks)	Post- CBIT (T2)
Informed Consent						
Medical History						
Neurologic Exam						
Pregnancy Test (if woman of childbearing age)						
Demographics						
Active rTMS						
Tele-CBIT						
YGTSS						
mRVTRS						
BDI						
BAI						

Y-BOCS					
ASRS					
GTS-QOL					
MEP					
CSP					
SICI					
HD-EEG					
fMRI					
Study Compensation					

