In order to participate in the study, patients will need to be present at the Fixel Neurologic Institute/University of Florida for 5 consecutive days at the beginning of the study, and will have to return in person for a single day after the 10 weeks of tele-CBIT.

Compensation:

Participants will receive \$60 for taking part in the study (compensation for their participation)- this compensation will be prorated, so that patients will receive \$20 in 3 equal installments, correlating with the T0, T1, and T2 outcome measure time periods.

Reimbursement:

In addition, participants who live a minimum of 50 miles from Gainesville will be offered a 4-night hotel stay of up to \$125 per night in Gainesville so that they can complete the 5 consecutive days at the beginning of the study without having to travel back home each night- this will be paid at the time the patient and family are staying at the hotel. Participants (and family members/caregivers who accompany them) will additionally be compensated up to \$150 (\$75 for gas and \$75 for food) during their visits to the Fixel Center/UF related to participation in this study. This will also be prorated so that they will receive \$25 for gas and \$25 for food in 3 equal installments at each of the outcome measure timepoints: T0, T1, and T2.

Data Safety Monitoring Plan: The research team monitors the patient safety and data collection of each study visit. The Data Safety and Monitoring Committee will meet once each year to review the recruitment, adverse events, data collection, and other aspects of the study. The Data Safety and Monitoring Committee will be notified of any adverse events that occur during the course of the study, within 2 business days of the specific adverse event. This will allow the DSMC to review any issues that arise in a timely manner. Breaches of confidentiality will also be monitored by the DSMC. If there is possible harm to subject safety or the possibility of, any harm due to something new that was learned during the study, the DSMC will be convened. If there is possible harm to subject safety or the possibility of, any harm due to something new that was learned during the study, the DSMC will be convened. [name]., [name] MD, and [name] MD will monitor the safety of the project yearly. [name] will serve as an independent health professional on the Data Safety Monitoring Committee.

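### Could the optional in-person CBIT session contaminate T1, since no rule says that T1 must come first?

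*Combined protocol and SAP*

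**What the plan says.** The Background section describes a four-day rTMS course followed by CBIT, with measurements at baseline (T0), after rTMS (T1) and after CBIT (T2). The Figure 1 caption repeats that CBIT follows rTMS and adds: "Clinical, physiology measures, and imaging will be collected at three time points". The columns of Figure 4 run screening, T0, rTMS, T1, CBIT, T2.

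Four other statements bear on the timing:

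- rTMS protocol: "Patients will receive 4 sessions each day on 4 consecutive days for a total of 16 sessions".
- CBIT protocol: patients are given "the option of having the first introductory CBIT sessions scheduled in-person since they will already be at the center for rTMS and outcome measures". The remaining sessions are by telemedicine, with 8 to 10 sessions over 10 weeks.
- The paragraph after Figure 4: patients must be present "for 5 consecutive days at the beginning of the study, and will have to return in person for a single day after the 10 weeks" (the CBIT period).
- Clinical Assessments, just before Figure 4: "All events related to the study procedure will take place within +/- 14 days of the expected timeline".

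Specific Aims 1 and 2 state hypotheses at T1 as well as T2, for example that "BOLD activity on fMRI will decrease over SMA at T1 and T2, compared to baseline".

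**The concern.** T1 is defined only as following rTMS. It is never defined as preceding CBIT. The reason given for the in-person option is that the patient is already on site for rTMS and outcome measures, and the only such occasion before CBIT is the five-day stay. The in-person session and T1 therefore fall within the same few days, and nothing in the text fixes which comes first. The blanket tolerance of 14 days either way seems to loosen the order further.

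T1 is the one point at which rTMS is read without CBIT. The study has a single arm and asks whether the two treatments act together. If some patients had a CBIT session before T1, their T1 change would mix the two, and only in those who chose the in-person option. That would add to the placebo response and natural tic fluctuation that T1 against T0 already carries. Dropping the affected T1 values afterwards would cost precision in a study of 20.

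**Working it through.** **1. The plan's own timing figure.** From the rTMS protocol section, a session is 6 trains × 5 min + 5 intervals × 1 min = 35 min. A day is 4 × 35 + 3 breaks × 10 = 170 min, which matches the stated figure. The whole schedule is 5 + 70 + 1 = 76 days, and 76 / 7 = 10.9 weeks, in line with the stated 11 to 12 weeks.

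**2. Does the stay force CBIT ahead of T1?** Five days on site less four rTMS days leaves one day free of rTMS. The documents do not say whether T0 or T1 takes it. The timed T1 items are EEG 60 min, fMRI 60 min and the drive to and from the scanner 2 × 10 min, 140 min in all. A CBIT session is about 60 min.

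| Layout | Last day, T1 and then CBIT |
|---|---|
| T0 shares the first rTMS day; T1 on the rTMS-free last day | 140 + 60 = 200 min |
| T0 on the rTMS-free first day; T1 after the last rTMS session | 170 + 140 + 60 = 370 min |

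The rating scales, the video and the single- and paired-pulse TMS have no stated duration and come on top. On the timed items, both layouts leave room for T1 and then CBIT in one day.

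**3. Could CBIT fall on the earlier rTMS days?** Those days look like convenient slots, but two sentences in the Background and one in the Figure 1 caption put CBIT after the rTMS course. A session on rTMS days 1 to 3 would depart from that order. What remains open is the interval from the last rTMS session to the end of T1.

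**4. The tolerance.** Taken in isolation, with CBIT starting on time and evenly spaced, a T1 delayed by 14 days could follow 14 / 70 = 20% of the CBIT period, which is 0.2 × 8 = 1.6 or 0.2 × 10 = 2 sessions. But the tolerance is measured from the expected timeline, which Figure 4 sets out with T1 ahead of CBIT. T1 also needs on-site equipment, and the plan has no on-site visit between the five-day stay and the return day after CBIT. A T1 that late would need a visit the plan does not contain.

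**5. Illustrative size.** The documents give no per-session effect and no standard deviation. The Background says that "randomized controlled studies have shown less than 40% reduction of tic symptoms in adult patients with TS". Assume that 40% accrues linearly over 8 to 10 sessions. One session is then 40 / 10 = 4 to 40 / 8 = 5 points in an affected patient. The effect on the group mean depends on the share affected (assumed):

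- 25%: 0.25 × (4 to 5) = 1.0 to 1.25 points
- 50%: 0.50 × (4 to 5) = 2.0 to 2.5 points
- 100%: 4 to 5 points

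This is not a strict ceiling. Accrual need not be linear, and the option is worded in the plural; two sessions would double the figures. An introductory session could equally do less than an average one. If affected T1 values were dropped, the standard error would rise by a factor of √(20/15) = 1.15 at 25% or √(20/10) = 1.41 at 50%.

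**The case for a change.** The strongest argument for a change is that column order in a schedule table does not oblige anyone. The sentences placing CBIT after rTMS do not mention T1, so CBIT could follow the last rTMS session and still come before T1 without breaching any of them. They also speak of tele-CBIT, whereas the in-person session is a separate option justified by presence at the center during rTMS and assessments. An ordering sentence would cost almost nothing, and no later analysis in a single-arm study could separate the two effects.

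The literal gap stands: no sentence makes T1 a condition for starting CBIT. The rest does not carry far. A T1 column headed as post-TMS and placed before the CBIT column has one natural reading, and a team that followed it would obtain a clean T1. Nothing in the documents shows that CBIT will precede T1, and the time budget does not push it there. The loss of precision arises only if affected values are excluded, which the plan does not propose. Separate windows for each event, extra date fields and a sensitivity analysis would be a heavy response to an interval of hours to a day or so in a pilot that, under Regulatory Approval and Statistics, is not powered and relies on descriptive statistics and ANOVA.

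**Conclusion.** This is a gap in wording that the study team can fill sensibly from what the plan already shows, so no change follows. Carried out in its displayed order, the plan gives a T1 free of CBIT. A written rule would only restate that order.

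The exposure is confined to patients who choose the in-person session and to the interval between the last rTMS session and the end of T1. Its size cannot be computed from the documents. The illustration of 4 to 5 points in an affected patient, and 1.0 to 2.5 in the mean at 25% to 50% affected, rests on linear accrual, a single session and assumed uptake, and the true figure is probably small. The comparison of T2 with T0 is unaffected. T1 against T0 is already limited by the open-label, single-arm design, and an ordering sentence would not remove that limit.

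One caveat applies: the drawing in Figure 1 and the cell marks in Figure 4 could not be read in the text version, so timing row by row was not checked.

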fMRI protocol: Functional MRI will be used to record Blood Oxygen Level Dependent (BOLD) activity changes in patients at rest, using protocols similar to other studies in the literature in the TS population³⁴, as well as fMRI studies conducted by our group in other movement disorder populations.⁴⁶ The fMRI procedure should last approximately 1 hour. A 32-channel head coil will be used on a 3T MRI scanner. Subjects will wear earplugs during the sessions to minimize discomfort due to scanner noise. Anatomical images will be acquired in 170 contiguous axial slices at $1 \times 1 \times 1$ mm resolution with a T1- weighted fast spoiled gradient-recalled sequence (repetition time (TR) = 6.8 ms; echo time (TE) = 3.3 ms; flip angle = 80°). Task-based functional MRI will be acquired in 46 axial slices at $3 \times 3 \times 3$ mm resolution using a single-shot gradient echo-planar imaging pulse sequence (TR = 2500 ms; TE = 30 ms; flip angle = 80°). Each functional scan will include 176 TR volumes. Cushions will be placed in the head coil around the subject's head to minimize head-motion with strapping if needed. Repetition times (TRs), that include head motion exceeding 0.5 mm from TR to TR, will be excluded. Open source platform Analysis of Functional NeuroImages (AFNI: Version 16.0.19) will be used for the whole brain analysis. A combined 1.0-mm motion exclusion criterion in the x-, y-, and z-planes will be used. The following preprocessing steps will be followed. The first three functional MRI volumes will be removed to

account for scanner magnetization equilibrium. Following that slice-timing correction, rigid-body volume registration, co-registration of the functional MRI scan to the T1-weighted anatomical scan, non-linear spatial warping of the functional MRI scan to the MNIavg152 template will be performed. Signal-to-noise ratio will be improved by spatial smoothing using a full-width at half-maximum Gaussian kernel of 8mm.

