Possible Benefits: The participant may or may not benefit from taking part in the study. All participants will undergo CBIT, which has previously been studied and is one of the first-line treatments for TS given its favorable efficacy^{11,48-49}, so participants may benefit from participation in CBIT. Half the subjects will receive active rTMS which may augment the CBIT sessions, leading to even further reductions in tic severity and frequency. The information gathered from this study will benefit the neurology department and the larger research community as we continue to seek the most efficacious treatments for Tourette's Syndrome.

Regulatory Approval and Statistics: The study will be approved by the University of Florida Institutional Review Board, and all subjects will provide written informed consent. The study is highly feasible given the relatively large number of patients with Tourette's that are seen at UF. This is a pilot study so it has not been powered for statistical significance. We will use descriptive statistics and ANOVA to run analysis on the data that has been collected.

Confidentiality: Information collected about the patient will be stored in locked filing cabinets or in computers with security passwords. Only certain people have the legal right to review these research records, and they will protect the secrecy (confidentiality) of these records as much as the law allows. These people include the researchers for this study, certain University of Florida officials, the hospital or clinic (if any) involved in this research, and the Institutional Review Board (IRB; an IRB is a group of people who are responsible for looking after the rights and welfare of people taking part in research). Otherwise the research records will not be released without participant permission unless required by law or a court order.

Researchers will take appropriate steps to protect any information they collect about participants. However, there is a slight risk that information about participants could be revealed inappropriately or accidentally. Depending on the nature of the information such a release could upset or embarrass them, or possibly even affect their insurability or employability.

If the results of this research are published or presented at scientific meetings, patient identity will not be disclosed.

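### The unspecified ANOVA, on its natural reading, wastes T0-T1 data when T2 is missed and leaves the Aim 2 correlation without an analysis; a model on all available visits plus one pre-named correlation is a cheap improvement

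*Combined protocol and SAP*

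**What the plan says.** The section Regulatory Approval and Statistics describes an unpowered pilot and gives one sentence of method: "We will use descriptive statistics and ANOVA to run analysis on the data that has been collected". It does not say which ANOVA, which visit contrasts, or how missing visits are handled. No other section does either.

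The hypotheses are more specific. Specific Aim #1 predicts that, "compared to baseline (T0), there will be greater reduction in tics" at T1 and T2. Specific Aim #2 predicts that "the change in TMS measures will significantly improve and BOLD activity on fMRI will decrease over SMA at T1 and T2", relative to baseline, and that these changes "will correlate with the clinical improvements as outlined in Specific Aim #1". No analysis is named for that last prediction. The fMRI protocol section gives preprocessing steps and names software that "will be used for the whole brain analysis", but no statistical test.

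On visits, T0 and T1 belong to the five-day stay at the start. For T2, patients "will have to return in person for a single day after the 10 weeks of tele-CBIT". An instalment of the compensation is tied to T2. The Enrollment and Clinical Assessments sections speak of four time points but list only T0, T1 and T2; those three are used here. The Background describes a single group in which everyone receives active rTMS. One sentence under Possible Benefits speaks of half the subjects; the single-group design is used here.

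**The concern.** The aims concern mean change from T0 within a small group, and Aim 2 adds an association between changes. A bare ANOVA settles neither.

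First, classical repeated-measures ANOVA needs a complete row per patient. T2 is the exposed visit, because it requires a separate trip after 10 weeks. A patient who misses it would drop out of the T0-T1 comparison too, although both of those measurements were taken. That costs precision. If patients who responded poorly to rTMS are the ones who stay away, it also makes the early effect look larger.

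Second, an ANOVA on visit means does not estimate how changes in two measures relate. With no correlation named in advance, a reader of the results could not tell a planned association from one picked after seeing the data.

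**Working it through.** **Inputs from the protocol.** Planned n = 20; three visits on the same patients; changes from T0 as the targets. The only planning figure is the enrolment count, which agrees with itself: 24 eligible - 4 declining = 20. Those 4 are refusals before enrolment and say nothing about later dropout.

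**Assumed inputs.** The documents give no SD, between-visit correlations or dropout rate. Results are in SD units. T2 loss is 2 to 4 of 20. Correlations are varied and listed as T0-T1 / T0-T2 / T1-T2.

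**1. Precision of T1-T0.** The half-width of a paired 95% interval is proportional to t(0.975, m-1)/sqrt(m), where m is the number of patients used.

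- m = 20: 2.093/4.472 = 0.468
- m = 18: 2.110/4.243 = 0.497, ratio 1.06
- m = 17: 2.120/4.123 = 0.514, ratio 1.10
- m = 16: 2.131/4.000 = 0.533, ratio 1.14

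So complete-case analysis widens the interval by 6%, 10% or 14% when 2, 3 or 4 patients miss T2.

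**2. Precision of T2-T0.** With equal correlations of 0.7, random loss of 4 and known covariance, the complete-case standard error is sqrt(2 x 0.3/16) = 0.194, against 0.188 for the likelihood model, a gain of 3%. When loss followed early response and the covariance was estimated, the simulated values were 0.192 complete-case and 0.196 for the model. The gain is negligible.

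**3. Bias when loss follows poor early response.** Suppose the 4 patients with the highest (T1-T0 change + noise of equal SD) miss T2. The four largest of 20 standard normal values average 1.332 in expectation, so the 16 who stay average -(4/16) x 1.332 = -0.333. Half the selection variance is noise, so the bias is -0.333/sqrt(2) = -0.235 times the SD of the change, which is sqrt(2(1 - r)) with r the T0-T1 correlation.

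- r = 0.9: 0.235 x 0.447 = 0.105
- r = 0.85: 0.235 x 0.548 = 0.129
- r = 0.7: 0.235 x 0.775 = 0.182
- r = 0.6: 0.235 x 0.894 = 0.210

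Simulation gives the same to within 0.002. Improvement is thus overstated by about 0.1 to 0.2 SD (with 2 lost, 0.06 to 0.12 SD). The mean over all 20 T0-T1 pairs is unbiased whatever drives T2 loss, provided T0 and T1 are complete. If loss is random, neither analysis is biased.

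**4. Bias in T2-T0.** This depends on what drives the loss (4 lost, simulated; negative means improvement overstated):

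| Correlations | Loss on T1-T0 change: complete-case / model | Loss on T2-T0 change: model | Loss on T2-T1 change: complete-case / model |
|---|---|---|---|
| 0.7/0.7/0.7 | -0.092 / about 0 | -0.14 | -0.092 / -0.137 |
| 0.85/0.7/0.7 | -0.063 / about 0 | -0.15 | -0.137 / -0.149 |
| 0.9/0.6/0.6 | -0.052 / about 0 | -0.17 | -0.184 / -0.170 |
| 0.6/0.6/0.9 | -0.186 / about 0 | -0.06 | -0.053 / -0.098 |

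The model removes the bias in the first case, where loss depends only on observed data plus noise. In the others a bias of about 0.06 to 0.17 SD remains. When loss follows the T2-T1 change, the model is worse than complete cases in three of the four rows.

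**5. Aim 2.** Counting RMT, CSP, SICI and SMA BOLD against seven clinical scales over two intervals gives 4 x 7 x 2 = 56 possible pairs, none named. Adding SMA connectivity would raise the count. For a single correlation, tanh(atanh(r) ± 1.96/sqrt(17)) gives a 95% interval of -0.05 to 0.72 at an observed r = 0.40, and 0.07 to 0.77 at r = 0.50.

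**The case against.** The strongest reply is that the faults are inferred. The plan says only ANOVA, applied to the data collected; it states no rule for dropping patients. That is right, and the point is therefore about what the plan leaves open.

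A reader might go further and infer that the visit contrasts will use a pooled error term without correction. At correlations of 0.9/0.6/0.6 or 0.85/0.7/0.7 that would cut T2-T0 coverage to 91.0% or 92.6%. A reader might also infer a one-way ANOVA that ignores pairing, with a heavy loss of power. Neither analysis is described anywhere, so those figures show only why the type should be stated.

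The second reply is that a mixed model is not essential. Paired differences on everyone with both visits recover all the T1-T0 data, the T2-T0 precision gain is negligible, and the model's near-zero T2-T0 bias rests on loss depending on observed data. All of this stands. Loss during 10 weeks of CBIT could well follow response to CBIT, where the model does not help. Hence paired differences are an acceptable alternative.

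Third, this is an unpowered pilot. That lowers the priority, but it makes estimates and intervals the main product, and Aim 2 still predicts significant improvement and correlation.

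Finally, 56 pairs tested at 5% would give 56 x 0.05 = 2.8 chance findings if all were null. The plan does not say all would be tested, so this is no forecast.

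**Conclusion.** The point holds as a cheap improvement, not as an error in a stated rule. Under the natural reading of ANOVA, and if 2 to 4 of 20 patients miss T2, the T1-T0 interval is 6% to 14% wider than with all T0-T1 pairs. If 4 are lost partly through poor early response, T1-T0 improvement is overstated by about 0.1 to 0.2 SD. Both are avoidable with data already collected. The dropout numbers and correlations are assumptions.

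For T2-T0 the benefit is limited to bias when loss depends on observed T0 and T1 data. With complete data the mean changes are identical under either method.

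The Aim 2 gap does not depend on dropout. A reader might infer that a mixed model closes it; a model for visit means does not, and a separate analysis is needed. Nor can either method show that rTMS augments CBIT, since the design has no comparator.

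**What to change.** Keep descriptive statistics, including for safety and tolerability under Aim 1c. Replace ANOVA with text to this effect:

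*For each scalar clinical, TMS, EEG and SMA summary outcome we will fit a linear mixed model with visit (T0, T1, T2) as a categorical effect, unstructured within-patient covariance, all available visits and Kenward-Roger degrees of freedom. We will report the T1-T0 and T2-T0 mean changes with 95% confidence intervals. If the model does not converge, we will report paired differences on all patients who have both visits.*

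If ANOVA is kept, use the same paired differences for the changes and apply a Greenhouse-Geisser correction to any overall test. Leave the whole-brain fMRI analysis as it is.

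Separately, for Aim 2, name one change-score correlation in advance, with the SMA or TMS measure defined. For example, pair SMA BOLD change with mRVTRS change from T0 to T1. Report it with its 95% interval and label all other correlations exploratory.

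The cost is three or four sentences and a few lines of code, with no new patients, visits or data. The downside is that the model estimates six covariance parameters (three variances, three covariances) from 20 patients, which is why the paired fallback is written in.
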